5.1.1.2 PFS

Progression-free survival is defined as the time (in months) from the date of randomization until the date of the investigator-assessed disease progression or death due to any cause, whichever comes first. Subjects who start to receive subsequent therapy before disease progression assessment will be censored at the date of the last progression-free assessment before subsequent therapy is initiated. A list of the definition of PFS events is presented in Table 5-2.

Subjects who are progression-free and alive as of the cutoff date will be censored at the date of the last progression-free assessment.

Table 5-2 Definition of PFS events

	Case	Date (if multiple cases apply, the earliest date is used)
Event	Progressive disease (PD) before the data cutoff date	Date of PD confirmation
	Death (PD not observed)	Date of death ^{*1}
Censoring	Non-PD or non-death at the time of data cutoff	Date of the last tumor assessment
	Unknown date of PD	Date of the last tumor assessment
	No tumor assessment after randomization	Date of randomization
	Another subsequent therapy for any reason other than PD	Date of the last tumor assessment before the start of subsequent therapy
	Evaluated as not evaluable (NE)	Date of the last tumor assessment immediately before evaluation
	Other	Date of the last tumor assessment

*1: If no tumor is assessed on the date of imaging assessment specified after the date of the last study treatment and a death event occurs before the acceptable limit of the imaging assessment day (the specified assessment day + 1 week), the event will be handled as a PFS event. If a death event occurs after the acceptable limit, the event is not handled as a PFS event.

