14.4 Progression Free Survival (PFS)

Progression free survival is defined as the time (in months) from the date of randomization until the date of the investigator-assessed radiological disease progression or death due to any cause, whichever comes first. Patients who receive post treatment before disease progression will be censored at the date of the last evaluable tumor assessment before post treatment is initiated. Patients who are alive with no disease progression at the time of the analysis will be censored at the date of the last confirmation as non-PD.

Event / Censoring	Case	Event date
Event	PD	the date of disease progression
	Death (without PD)	the date of death
Censoring	Non-PD at the time of analysis	the date of the last tumor assessment
	The date of PD is unknown	the date of the last tumor assessment
	Patient without any tumor assessment after randomization	the date of randomization
	Patient receive other post treatment for a reason other than PD	the date of the last tumor assessment
	Other	the date of the last tumor assessment

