5.2. Common Considerations for Statistical Analysis

5.2.1. Data Handling

5.2.1.1 Handling of Longitudinal Data

5.2.1.1.1 Calculation of Number of Days and Period

In this statistical analysis plan, the number of days and period will be consistently calculated using the following formulas unless otherwise specified:

- After the reference date Day n = target date – reference date + 1
- Before the reference date Day n = target date – reference date

Accordingly, the start date of treatment is Day 1, the day following the start of treatment is Day 2, and the day before the start of treatment is Day –1. The period is 1 day when the target date is just the reference date and 2 days when the target date is the date following the reference date.

If the month is missing in a date used for the calculation, the number of days and period is regarded as missing. If only the day is missing, it is replaced with the first day before calculation (e.g., April xx, 2016 → April 1, 2016). Only when the date of death is missing (year and month observed) and the date of the last survival confirmation in the same year and month is known, the date of death is regarded as the date following the last survival confirmation.

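### Both PFS tables censor a patient whose progression is known but undated and leave out that patient's later death, against the prose definition of PFS

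*SAP*

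**What the plan says.** **Prose.** Protocol 14.4 runs PFS from randomization "until the date of the investigator-assessed radiological disease progression or death due to any cause, whichever comes first". SAP 5.1.1.2 gives the same definition without the word for radiological. Apart from patients who start other treatment before progression, the patients whom the prose sends to censoring are those still alive and free of progression. The protocol has "Patients who are alive with no disease progression at the time of the analysis will be censored". The SAP has "Subjects who are progression-free and alive as of the cutoff date will be censored at the date of the last progression-free assessment".

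**Tables.** Each document then lists events and censorings by case. Under censoring, the protocol has "The date of PD is unknown" and the SAP has "Unknown date of PD", both dated at the last tumour assessment. The death rows begin "Death (without PD" in the protocol and "Death (PD not observed" in the SAP. The SAP table also takes the earliest date when several cases apply.

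**Partial dates.** SAP 5.2.1.1.1 says "If only the day is missing, it is replaced with the first day before calculation". If the month is missing, the period is treated as missing. These are defaults that give way to a specific rule elsewhere. SAP 5.2.1.2 says that missing data are not imputed.

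**The concern.** A patient known to have progressed is not progression-free, so the prose gives no ground for censoring. Under the tables this patient is censored, and a later death fits no event row because progression was observed. In the SAP, the earliest-date instruction also puts the last-assessment date ahead of the death. A patient with two qualifying events is therefore analysed as having none.

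The censoring depends on outcome: the patient leaves the risk set at the last clean assessment because progression followed it. PFS is lengthened in any arm where this happens, and the hazard ratio shifts if it happens more often in one arm. SAP 7.1.2 carries the Section 6 analyses over to PFS, but those vary the strata, the population and the use of the cutoff date. None varies this rule, so none would show its effect.

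**Working it through.** The plan gives no figure on this point, so there is none to reproduce. The check sets the rules against one patient and then sizes the effect under assumed rates.

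**One hypothetical patient.** Randomized 10 January 2016, last non-PD assessment 2 March 2016 (taken as an extra scan), death 20 June 2016. Day number = date − randomization date + 1 (SAP 5.2.1.1.1); months = days / 30.4375 (SAP 5.2.1.1.2).

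- 2 March: 52 + 1 = Day 53, 1.74 months
- 1 April: 82 + 1 = Day 83, 2.73 months
- 20 June: 162 + 1 = Day 163, 5.36 months

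| What is recorded about PD | Rule followed | Result |
|---|---|---|
| April 2016, day missing | Date read as unknown, Table 5-2 | Censored, Day 53 |
| April 2016, day missing | Day set to the 1st, 5.2.1.1.1 | Event, Day 83 |
| Month also missing | Table 5-2 | Censored, Day 53; death ignored |
| Month also missing | Prose, death counted | Event, Day 163 |

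The last two rows are the conflict between table and prose. The first two differ only because neither document says whether a date lacking just the day is unknown.

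**Size.** Inputs: PFS medians of 8.3 and 5.6 months for S-1/LV/L-OHP and S-1/CDDP in the earlier phase II study (Protocol 2.4), and scans every 42 days, which is 42 / 30.4375 = 1.38 months. Assumed: exponential PFS, 36 months of follow-up, and a share q of PFS events with undated progression. If every patient in the 650-patient FAS had an event, q of 1% to 5% would be about 7 to 33 patients. The simulation used 200,000 patients per arm, kept other event times exact, and censored each affected patient at the preceding scan. The hazard ratio is the ratio of events per unit of person-time; without undated progression it is 5.6 / 8.3 = 0.675.

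| q, TAS-118/L-OHP | q, S-1/CDDP | HR | Medians (months) |
|---|---|---|---|
| 0 | 0 | 0.675 | 8.26 / 5.59 |
| 1% | 1% | 0.674 | 8.39 / 5.64 |
| 2% | 2% | 0.674 | 8.46 / 5.70 |
| 5% | 5% | 0.670 | 8.75 / 5.85 |
| 5% | 0 | 0.643 | 8.70 / 5.60 |
| 0 | 5% | 0.708 | 8.30 / 5.88 |

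The two values for the experimental arm at q = 0 (8.26 and 8.30) show simulation noise of about 0.05 month.

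Hand checks agree. Removing a share q of events lowers the estimated hazard by about (1 − q), so the median becomes about 8.3 / 0.95 = 8.74 and 5.6 / 0.95 = 5.89 months. The HR is multiplied by about (1 − q_A) / (1 − q_B): 0.675 × 0.95 = 0.641 for 5% against 0, and 0.675 / 0.95 = 0.711 for 0 against 5%.

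**The case against.** The strongest defence is that the table fills a gap. Both definitions run to the date of progression, so without a date the prose yields no time. The SAP refers to Table 5-2 for the definition of events, and protocol and SAP agree on the row, so the rule is consistent and prespecified. All of that is true, but it does not remove the conflict. The prose would still count the later death, and it gives no reason to censor someone who is not progression-free. It could also be said that undated progression is not radiological progression in the protocol's sense. The death would then be the event, and the tables would still exclude it.

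A reader might infer three stronger things that the documents do not support.

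- *SAP 5.2.1.1.1 contradicts the table.* It need not. It is a default, and *unknown* can be read as what remains when the month or year is missing. What is left is an undefined term and a missing cross-reference.
- *Anyone who progresses and then dies is lost.* Progression with a date is an event on that date. The problem is confined to undated progression.
- *The rule favours one arm.* Scans are 6-weekly from randomization in both arms, whatever the cycle length. Tumour follow-up may stop on a change of hospital (Protocol 13.1.3), but that mainly produces patients with no recorded progression.

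It also stands that the rates above are assumed, that CT or MRI assessment should make undated progression uncommon, and that equal shares hardly move the HR. Separately, the footnote to Table 5-2 excludes some deaths after a missed scan window in patients without observed progression. That is a different rule, which this point leaves alone.

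**Conclusion.** The point holds in limited form. For progression that is known but undated, both tables censor a known event and leave out the later death, contrary to the prose of the documents they belong to. This is a stated rule that produces informative censoring.

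Its effect on the medians is small: about half a month or less in either arm at the assumed upper share of 5%. Its effect on the HR is close to nil at equal shares. At 5% against none, the HR moves by about 0.03 in favour of the arm with more undated progression. These sizes rest on assumed shares, exponential PFS and phase II medians. PFS is a secondary endpoint, and the OS test does not use this rule. The change is worth making because it is cheap and no planned analysis would reveal the effect.

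**What to change.** 1. Define an unknown progression date as one with the month or year missing after SAP 5.2.1.1.1 has been applied. Where only the day is missing, use the first of the month, but not earlier than the day after the last non-PD assessment. The SAP already protects a partial death date in this way.
2. Replace the censoring row so that known progression with an unknown date is an event. Date it at the first scheduled scan after the last non-PD assessment, not before any period in which progression is known to have occurred, and no later than the first record of progression, the start of new therapy, or death. Patients who start new therapy before progression stay under the existing row for them.
3. State this as an exception to the no-imputation rule in SAP 5.2.1.2.
4. Keep the present censoring rule as a sensitivity analysis.

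For the patient above, a date lacking only the day gives an event at Day 83. With the month also missing and only 2016 known, the next scheduled scan is Day 2 × 42 + 1 = 85 (2.79 months), before the death at Day 163, provided no earlier record of progression or new therapy exists.

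Cost: SAP wording and one programming rule, with no new data. The protocol table must be aligned by amendment, or the change listed in SAP 1.3, as was done for the FAS definition. PFS medians may become slightly shorter.

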14.1.1.3 Evaluation of Response in Target Lesions

The response in target lesions should be evaluated using the 5-grade scale shown below.

Complete Response (CR):

Complete disappearance of non-nodal target lesions, and the short axes of all nodal target lesions below 10 mm (an assessment of CR with the sum of diameters being above 0 is possible if nodal lesions have been included in target lesions before the study treatment).

Partial Response (PR):

A decrease of at least 30% in the sum of the diameters of target lesions in comparison with the baseline value.

Stable Disease (SD):

The absence not only of tumor shrinkage corresponding to CR or PR but also of tumor growth corresponding to PD.

Progressive Disease (PD):

An increase of at least 20% and at least 5 mm in length in the sum of the diameters of target lesions in comparison with the smallest value among the sums obtained previously (including the baseline value).

Not Evaluable (NE):

Lack of examination for any reason; response corresponding to none of CR, PR, SD, and PD.

The diameters of target lesions should have their actual measurements recorded even when they have become very small (e.g. 2 mm). When the diameter has become “too small to measure”, the measurement should be recorded as 0 mm if the lesion is considered to have disappeared, or a default value of 5 mm should be assigned if the lesion is believed to be present.

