14.1.2 Assessment of Overall Response

Assessments will be based on the definitions provided in Table 14.1.2-1 and Table 14.1.2-2 below.

Table 14.1.2-1 Time Point Response for Patients with Target (+/- Non-target) Disease

Target Lesions	Non-target Lesions	New Lesions	Overall Response
CR	CR	No	CR *
CR	Non-CR/Non-PD or Not all evaluated	No	PR
PR	Non-PD or Not all evaluated	No	PR
SD	Non-PD or Not all evaluated	No	SD
Not all evaluated	Non-PD	No	NE
PD	Any	Yes or No	PD
Any	PD	Yes or No	PD
Any	Any	Yes	PD

* For CR, tumor marker must have been under upper limit of normal.

Table 14.1.2-2 Time Point Response for Patients with only Non-target Disease

Non-target Lesions	New Lesions	Overall Response
CR	No	CR *
Non-CR/Non-PD	No	Non-CR/Non-PD
Not all evaluated	No	NE
Unequivocal PD	Yes or No	PD
Any	Yes	PD

* For CR, tumor marker must have been under upper limit of normal.

When no imaging/measurement is done at all at a particular time point, the patient is not evaluable (NE) at that time point. If only a subset of lesion measurements are made at an assessment, usually the case is also considered NE at that time point, unless a convincing argument can be made that the contribution of the individual missing lesion(s) would not

change the assigned time point response.

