1.3. Changes from Protocol

The full analysis set (FAS) is defined as “patients in as-treated (AT) population who have gastric cancer at randomization” in the protocol version 3.0, but the definition is changed to “patients in AT population who have advanced gastric cancer at randomization” in this statistical analysis plan. Since this study involves patients with advanced gastric cancer as specified in the primary objective, the protocol has not been revised, and the detailed definition of FAS is specified in the statistical analysis plan as determined in the discussion with medical advisor and the statistical advisor.

2. Main Statistical Considerations in the Study Design and Planned Sample Size

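### Read literally, SAP Table 5-2 lets an intermediate not-evaluable assessment censor PFS ahead of a later observed progression or death

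*SAP*

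**What the plan says.** **SAP 5.1.1.2, Table 5-2.** One censoring case is "Evaluated as not evaluable (NE"), dated at the "Date of the last tumor assessment immediately before evaluation". The row sets no condition on how many assessments are NE or on what is seen afterwards. The date column is headed "Date (if multiple cases apply, the earliest date is used"). The prose of the section runs PFS to progression or death and does not mention NE.

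**Protocol 14.1.2 and 14.1.1.3 (what counts as NE).** "When no imaging/measurement is done at all at a particular time point, the patient is not evaluable (NE) at that time point". For partial assessments: "If only a subset of lesion measurements are made at an assessment, usually the case is also considered NE at that time point", with an exception where the missing lesions would not alter the response. At target-lesion level, NE is "Lack of examination for any reason; response corresponding to none of CR, PR, SD, and PD".

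**Protocol 14.4.** Its PFS table has neither an NE row nor an earliest-date rule. Progression is an event at its own date. A patient alive without progression "will be censored at the date of the last confirmation as non-PD".

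**Protocol 11.2, schedule tables.** Tumor assessment continues every 6 weeks in patients without PD, so one NE time point does not end scanning.

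**SAP 1.3 and 7.1.2.** The list of changes from the protocol begins "The full analysis set (FAS) is defined as" and covers only that definition. The PFS analyses are carried over from SAP section 6, and none of them varies the NE rule.

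**The concern.** An NE time point is a gap in observation. It does not end observation, because the protocol goes on scanning and later progressions are recorded. A rule that censors at the assessment before the NE, and gives that date priority, discards events that were actually seen. The protocol and the SAP then give different PFS outcomes for the same patient, and the list of changes does not say so.

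Three things are at stake:

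- **Precision.** Fewer PFS events mean a wider interval for the hazard ratio. The risk of an NE accumulates with each scan, so the arm with longer PFS would lose more events even at equal NE rates.
- **Possible bias.** If scans are missed or incomplete because the patient is deteriorating, the censoring is informative. The trial is open-label and PFS is investigator-assessed, so this cannot be ruled out.
- **Reproducibility.** Two programmers could derive different PFS datasets from the same table.

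**Working it through.** Neither document states a PFS event count, a PFS power or an NE rate, so there is no plan figure to reproduce. The check is a comparison of texts, followed by an illustration of size.

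**1. One patient under both documents.** SD at week 6, NE at week 12, PD at week 18.

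| Rule | Cases that apply | Result |
|---|---|---|
| Protocol 14.4 | PD (week 18) | Event at week 18 |
| SAP Table 5-2, literal | PD (week 18); NE (week 6) | Earliest date: censored at week 6 |

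The NE date always precedes a later PD or death, so under the header it always wins.

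**2. When NE arises (protocol 14.1.2, no PD and no new lesion).**

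| Situation | Time point response |
|---|---|
| No imaging | NE |
| Only a subset of lesions measured | Usually NE |
| Target lesions not all evaluated | NE |
| Non-target disease only, not all evaluated | NE |
| Target CR or PR, non-target not all evaluated | PR |
| Target SD, non-target not all evaluated | SD |

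**3. Closed form for the share of progressors affected.** Inputs:

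- Median PFS 8.3 and 5.6 months (phase II figures in protocol 2.4), taken as exponential.
- A scan every 6 weeks, which is 42/30.4375 = 1.380 months.
- Independent NE probability p per scan (an assumption).

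The chance of staying progression-free over one interval is q = 2^(−1.380/median), which is 0.891 for 8.3 months and 0.843 for 5.6 months. PD would first show at scan k with probability q^(k−1)(1−q). Summing over k:

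- Share with an NE before the scan that shows PD = qp/(1−q+qp).
- Share with an NE at or before that scan = p/(1−q+qp).

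At p = 2%:

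- Median 8.3 months: 0.0178/(0.1088+0.0178) = 14.1%, and 0.02/0.1266 = 15.8%.
- Median 5.6 months: 0.0169/(0.1570+0.0169) = 9.7%, and 0.02/0.1739 = 11.5%.

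**4. Events lost with limited follow-up.** Simulation with 325 patients per arm (FAS target) and 19 to 38 months of follow-up (from the 19 + 19 months in protocol 16.4). It compares censoring before the first NE with ignoring NE. An NE at the scan that would have shown PD also counts.

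| Assumed NE per scan | Arm A (8.3 months) | Arm B (5.6 months) |
|---|---|---|
| 1% | 6.6% lost | 5.6% lost |
| 2% | 290 to 253 (12.8%) | 312 to 280 (10.3%) |
| 5% | 289 to 208 (27.9%) | 312 to 240 (23.1%) |
| 10% | 45.1% lost | 39.5% lost |

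A repeat of the simulation agrees to within 0.3 percentage points. The losses are somewhat below the at-or-before closed form because limited follow-up removes the latest progressions, which have the most scans at risk.

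**5. What this does to precision.** With SE(log HR) ≈ √(1/d_A + 1/d_B):

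- At 2%: √(1/290+1/312) = 0.0816 becomes √(1/253+1/280) = 0.0867, an interval about 6% wider on the log scale.
- At 5%: √(1/289+1/312) = 0.0816 becomes √(1/208+1/240) = 0.0947, about 16% wider.

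With NE independent of outcome, the simulated Kaplan–Meier medians are the same under both rules at all four rates.

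**The case against.** The strongest reply is that the censoring rows describe final states of patients without an event. On that reading the NE row only says that, when the last assessment is NE, censoring steps back to the one before. This would implement the protocol's last confirmation of non-PD, because an NE scan confirms nothing. The SAP prose supports it, since it never lets NE end PFS. Nor can the header be applied mechanically everywhere. A patient who dies before any scan also meets the no-assessment row, dated at randomization, although the footnote counts a death inside the scan window as an event.

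This reading is plausible and may be what was intended, but the SAP does not state it. The header cannot simply be confined to event rows either. It is needed across event and censoring rows so that censoring for subsequent therapy precedes a later PD. The footnote concerns deaths and does not restore a later PD.

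Four narrower objections:

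- **Missed scans.** The SAP row speaks of an evaluation, and a scan never done is not clearly one. Including missed scans means reading protocol 14.1.2 into the row. That inference is reasonable but not certain.
- **Incomplete scans.** A reader might infer that any incomplete scan is NE. It is not: see the last two rows of the table in step 2, and the exception for partial scans.
- **Undeclared change.** Protocol 14.4 has a catch-all censoring row, and protocol section 16 leaves technical detail to the SAP. That permits elaboration, but turning a protocol-defined event into a censored time goes further than detail.
- **Bias.** A reader might infer from the larger loss in Arm A that the rule works against that arm. Unequal event loss alone does not show bias: with NE independent of outcome the hazard ratio is nearly unchanged. Protocol 11.4 also provides for extra scans when PD is strongly suspected, which may reduce informative gaps.

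**Conclusion.** The point holds as a defect of wording with a real analytic consequence if the table is followed literally. An unqualified NE row combined with an earliest-date header censors patients whose later PD or death was observed, contrary to protocol 14.4 and without an entry in SAP 1.3.

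The likely cost is lost PFS events and precision: about 6–7% of events at 1% NE per scan, 10–13% at 2% and 23–28% at 5%. These figures rest on assumed NE rates, exponential PFS with the phase II medians, and NE independent of outcome. Bias is possible if NE follows deterioration, but the documents give no basis for quantifying it.

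Two stronger conclusions are not supported. The documents do not establish that the sponsor intends to censor at every NE. They also list the secondary endpoints without ranking them, so PFS cannot be called the main one. The primary OS analysis is unaffected. The table should be corrected before PFS is derived.

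**What to change.** In SAP Table 5-2, keep the NE row but restrict it: last available assessment is NE and there is no later PD or death; censor at the last evaluable non-PD assessment. Deleting the row is not the better option. A patient whose final scan is NE would then fall to the general last-assessment rows, and the NE scan itself could become the censoring date.

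Add three statements:

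- An NE or missed time point followed by PD is an event at the PD date, as in protocol 14.4.
- NE alone does not remove a later death. Say how this works alongside the existing footnote on deaths after a missed scan.
- The earliest-date rule does not let an intermediate NE override a later event. Its use for subsequent therapy is unchanged.

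Record any remaining departure from protocol 14.4 in SAP 1.3.

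The cost is one table row, a clarification of the header and the matching dataset derivation. No new data are needed.
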